4.6.2 Other Prohibited and/or Restricted Treatments

Prohibited and/or restricted medications taken prior to study drug administration and during the study are described below, and washout requirements are provided in [Appendix 4](#). All medications taken within 30 days prior to screening must be recorded on the eCRF.

1. Prior exposure to BOS161721
2. Patients who have received treatment with anti-CD20 monoclonal antibodies within 24 weeks of screening
3. Patients who have received treatment with cyclophosphamide within the 24 weeks prior to screening
4. Patients who have received treatment with cyclosporine (with exception of ophthalmic use), any other calcineurin inhibitor or other immunosuppressive medication not specified in the inclusion criteria within 4 weeks for oral use or 8 weeks for topical use of screening
5. Patients who are currently receiving or are scheduled to receive plasmapheresis or lymphapheresis therapy, or have received such therapy within 24 weeks prior to screening
6. Patients who have received any live vaccines within 30 days of screening. Note: Furthermore, live vaccines should not be used during the course of the study and within the 2 months following last dose. Other inactivated vaccines such as tetanus, etc., may be used according to local guidelines during treatment period
7. Patients who are scheduled or anticipated to have elective surgery during the course of the study
8. Initiation of new immunosuppressant or anti-malarial agent is not permitted. Note: Dose reduction or replacement may be allowed due to intolerability or shortage for patients on a stable dose prior to study initiation

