Blood samples were collected at every in-house study visit for BOS161721 concentration determinations. Blood samples were also collected for determination of IL-21 plasma levels (free and total). Safety was assessed based on the occurrence of treatment-emergent AEs, hepatic function abnormality, and acute and delayed hypersensitivity reactions. Other safety variables included ECGs, vital signs (blood pressure [BP], heart rate, and temperature), safety laboratory assessments, blood sampling for ADAs, total IgG and immunoglobulin M (IgM) levels, CD4+ count, and full and targeted physical examinations. Overall, there were no clinically significant findings from this study. Adverse events reported as related to the study drug, particularly infections, were expected for the compound, and there were no clinically relevant changes in laboratory and ECG results or vital signs. There was 1 serious adverse event (SAE; death due to pulmonary embolism) that occurred 127 days after a single administration of 240 mg SC dose of BOS161721. The causality of this single SAE was not attributed to study drug and further information can be found in the Investigator's Brochure. Final PK data from the SAD study demonstrates BOS161721 has a mean $t_{1/2}$ ranging from 80 to 87 days for doses of ≥ 30 mg in healthy subjects.

[figure not shown]

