1.2.3 Study Dose Selection

Doses have been selected for the multiple ascending dose (MAD) phase 1b portion based on a 90 day safety, tolerability, PK, and PD data review from the phase 1 SAD study (BOS161721-01); the SDMT reviewed the blinded safety data from subjects for each dose cohort (8 cohorts, evaluating 1 [IV], 3 [SC], 10 [SC], 22 [IV], 30 [SC], 60 [SC], 120 [SC], or 240 [SC] mg), along with the accumulated safety and available PK/PD data

from all subjects in the previous dose cohorts, to make a decision on whether to proceed to the next higher dose level, repeat a dose level, or stop dose escalation. Overall, there were no clinically significant safety or tolerability findings from this study.

Based on the Day-90 interim cut of the PK and biomarker data in the BOS161721-01 study, the recommended doses for evaluation in the MAD portion of this study are 20, 60, and 120 mg SC monthly. This dose recommendation is supported by evidence of linear PK with BOS161721 resulting in a median first time to maximum concentration (T_{max}) of 6 days and an apparent terminal half-life of 44 days. Furthermore, pSTAT3 suppression, a marker of IL-21 target engagement, follows a similar time course of the mAb levels, with maximal and sustained suppression apparent with doses greater than 30 mg SC (Figure 1).

Figure 1. Individual pSTAT3 C_{min} Levels Versus Dose

IV = intravenous, pSTAT3 = phosphorylated signal transducer and activator of transcription 3;
SC = subcutaneous

All doses selected for the MAD portion are projected not to exceed the mean exposure of that achieved following the highest single dose of 240 mg SC administered in the phase 1 SAD study. Cohort 1 will include randomized treatment to the 20 mg dose. Based on the staggered study design, the data monitoring committee (DMC) will perform a scheduled review of safety data and sequentially consider dose escalation for Cohorts 2 and 3. In addition, the DMC and Boston Pharmaceuticals will conduct a data

review to determine which dose will be carried forward into the proof of concept (POC) phase 2 portion. This POC dose decision will be based on evaluation of the PK, safety (inclusive of dose-limiting toxicity [DLT]), and tolerability data (and available PD/biomarker data) from Cohorts 1, 2 and 3 from the MAD portion (see [Section 3.1.2.1](#) for the chosen POC dose and justification).

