1.2.5.4 Infections

BOS161721 is expected to diminish the activity of T-cell, B-cell and NK-cell lines. Like other medications modulating immune response, BOS161721 may increase the potential risk for infection, including serious infections. IL-21 produced by CD4+ T-cells is required to sustain the anti-viral function of CD8+ T-cells against chronic viral infections. Nonclinical evidence suggests that the risk of chronic viral infection recurrence or increased severity may occur with IL-21 inhibition.³⁵

These conditions will be fully characterized with clinical descriptions and routine laboratory and/or specialty testing and treated where indicated with appropriate local standard of care.

Patients with a history of opportunistic infection, including recurrent or severe disseminated herpes zoster or disseminated herpes simplex within the last 3 years, or any other underlying pathology predisposing to serious infection, are excluded from studies with BOS161721 (for further details please refer to the current IB for BOS161721).

Patients will be assessed for hepatitis B, and C, and HIV-1/2 combination, at screening.

Cryptosporidium Infection

Cryptosporidium infection was noted in patients with an IL-21 receptor loss-of-function gene mutation and similar findings of cryptosporidium infection have been observed in immunosuppressed liver transplant and human immunodeficiency virus patients.^{36,37} Since BOS161721 is expected to diminish the immunosurveillance activity of T-cell, B-cell, and NK-cell lines, a similar risk is biologically plausible with prolonged exposure to BOS161721.

Since the risk of opportunistic cryptosporidium infection increases with low levels of CD4+ T-cells,³⁷ patients with a CD4+ count < 500 cell/mm³ were excluded from the phase 1 SAD study (BOS161721-01). Patients with CD4+ count < 350 cells/mm³ and CD4+ count < 150 cells/mm³ will be excluded from the MAD and POC parts of the study, respectively. Patients exposed to investigational product who develop diarrhea during the course of the study should immediately undergo an assessment for opportunistic infection including stool for ova and parasites and stool examination for cryptosporidium. Positive cryptosporidium in stool sample at screening is an exclusion. Treatment by the Investigator where indicated should be guided by findings and be consistent with local standard of care.

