1.2.5.9 Potential Risk to Fetal Development

No data on preclinical reproductive toxicity are available at the time of this study.

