27. Any other severe acute or chronic medical or psychiatric condition, including recent (within the past year) medical conditions (e.g., cardiovascular conditions, respiratory illnesses) that may increase the risk associated with study participation or investigational product administration or may interfere with the interpretation of study results and, in the judgment of the Investigator, sponsor or sponsor's designee, would make the patient inappropriate for entry into this study.
28. Investigational site staff members directly involved in the conduct of the trial and their family members, site staff members otherwise supervised by the Investigator, or patients who are employees of the sponsor or directly involved in the conduct of the trial.
29. Currently participating in, or who have participated in other interventional (drug or device) clinical study within 30 days or 5 half-lives of baseline, whichever is longer.
30. Recent (within the past 12 months) or active suicidal ideation or behavior based on patient responding "yes" to question 3, 4 or 5 on the C-SSRS.
31. Current or pending incarceration.
32. Current or pending compulsory detainment for treatment of either a psychiatric or physical (e.g., infectious disease) illness.
33. Currently taking a total daily dose of > 30 mg morphine or morphine equivalent (see [Appendix 7](#)).
34. Body mass index (BMI) \geq 40.0.

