4.7.2 Contraception

WOCBP must agree to follow instructions for method(s) of contraception for the duration of treatment with study drug plus 52 weeks, due to the mean terminal $\frac{1}{2}$ life of the study drug.

Men who are sexually active with WOCBP must agree to follow instructions for method(s) of contraception for the duration of treatment with study drug plus 52 weeks, due to the mean terminal $\frac{1}{2}$ life of the study drug.

Investigators shall counsel WOCBP and men who are sexually active with WOCBP on the importance of pregnancy prevention and the implications of an unexpected pregnancy. Investigators shall advise WOCBP and men who are sexually active with WOCBP on the use of highly effective methods of contraception. Highly effective methods of contraception have a failure rate of < 1% when used consistently and correctly.

- Patients must agree to either complete abstinence, defined as a complete avoidance of heterosexual activity, or the use of 2 methods of effective contraception from the following:
- Male condoms with spermicide
- Diaphragm with spermicide
- Cervical cap with spermicide
- Hormonal methods of contraception including combined oral contraceptive pills, vaginal ring, injectables, implants, patches and intrauterine devices (IUDs) such as Mirena® by patients who are WOCBP or a male patient's WOCBP partner. Women who are partner of men who are patients participating in the study may use hormone-based contraceptives as one of the acceptable methods of contraception since they will not be receiving study drug
- IUDs, such as ParaGard®
- Vasectomy
- Note: Women who are abstinent while participating in the study must continue to have pregnancy tests. Acceptable alternate methods of highly effective contraception must be discussed in the event that the patient chooses to forego complete abstinence

- Azoospermic men and WOCBP who are continuously not heterosexually active are exempt from contraceptive requirements. However, WOCBP must still undergo pregnancy testing

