16.4 Appendix 4: Medication Washout Periods

WASHOUT TIMES OF MEDICATIONS BASED ON 5 HALF-LIVES

Medication	Discontinuing Prior to Signing Consent
Abatacept (CTLA4Ig)	24 weeks
Alefacept	12 weeks
AMG 623 (blisibimod)	24 weeks
Anifrolumab	12 weeks
Atacept (TACI-Ig)	12 weeks
Belimumab	24 weeks
Cyclophosphamide	24 weeks
Cyclosporine (except for CSA eye drops)	4 weeks for oral and 8 weeks for topical
Danazol	4 weeks
Dapsone	4 weeks
Eculizumab	12 weeks
Efalizumab	12 weeks
Epratuzumab	24 weeks
Intravenous globulin	4 weeks
Leflunomide	8 weeks (4 weeks for washout with cholestyramine)
Lenalidomide with cholestyramine	8 weeks
Lupuzor	12 weeks
Memantine	4 weeks
Natalizumab	24 weeks
Ocrelizumab	48 weeks (or 24 weeks with recovery of B cell)
Pimecrolimus	4 weeks
Plasmapheresis	24 weeks
Retinoids (oral or topical)	4 weeks
Rituximab	48 weeks (or 24 weeks with recovery of B cell)
Sirolimus	4 weeks
Tacrolimus	4 weeks
Thalidomide	8 weeks
Tocilizumab	12 weeks

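### The live-vaccine ban in Protocol Section 4.6.2 lapses about one half-life after the last dose, too early for a drug with an 80–87 day half-life

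*Protocol*

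**What the plan says.** Section 4.6.2, item 6, excludes patients who had a live vaccine within 30 days of screening and adds that "live vaccines should not be used during the course of the study and within the 2 months following last dose". It gives no reason for two months. I found no other live-vaccine restriction in the current protocol text.

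The last scheduled dose is Day 180 and the last visit is Day 270 (Section 3.1). Sections 5.5 and 6.2.1.1 describe that last visit as 90 days after dosing. Section 3.5 places an individual patient at end of study on withdrawal, premature discontinuation or completion of all procedures.

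Two half-lives are printed. Section 1.2.2.3 gives the final single-dose result, a mean "ranging from 80 to 87 days for doses of ≥ 30 mg in healthy subjects". Section 1.2.3 gives the figure from the Day-90 interim cut, "an apparent terminal half-life of 44 days". The same section describes the pharmacokinetics as linear and reports maximal, sustained pSTAT3 suppression at subcutaneous doses above 30 mg.

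On the hazard, Section 1.2.5.4 states that "BOS161721 is expected to diminish the activity of T-cell, B-cell and NK-cell lines" and that infection risk, including serious infection, may rise. On contraception, Section 4.7.2 requires precautions "for the duration of treatment with study drug plus 52 weeks, due to the mean terminal" half-life of the drug.

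**The concern.** The sponsor accepts that live vaccines and this drug should be kept apart, since it wrote a ban. What matters is whether the ban lasts as long as the drug's effect. A two-month tail is short against a half-life of nearly three months, and the protocol ties its contraception interval, which also runs from the end of treatment, to that half-life.

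If the ban ends while IL-21 is still substantially blocked, a patient who follows the protocol exactly may receive a live vaccine while T-, B- and NK-cell activity is still expected to be reduced. The stake is patient safety after the last visit. No efficacy or safety analysis depends on it.

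**Working it through.** **Inputs.** Last dose Day 180, last visit Day 270, seven doses 30 days apart (Section 3.1). POC dose 120 mg (Section 3.1.2.1). Half-life *h* = 80–87 days (Section 1.2.2.3) or 44 days (Section 1.2.3). Contraception interval 52 weeks = 364 days (Section 4.7.2). Two months is taken as 60 days.

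**The plan's own interval.** 270 − 180 = 90 days, which matches the 90 days stated in Sections 5.5 and 6.2.1.1. The two-month tail ends near Day 180 + 60 = Day 240, so for an on-schedule completer the study period sets the end of the ban.

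**Fraction of the end-of-dosing load remaining after *t* days.** Half-lives elapsed = *t*/*h*; fraction = 0.5^(*t*/*h*).

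| Time after last dose | *h* = 80 | *h* = 87 | *h* = 44 |
|---|---|---|---|
| 60 days (early leaver, no 90-day visit) | 0.75 half-lives, 59.5% | 0.69, 62.0% | 1.36, 38.9% |
| 90 days (completer) | 1.125, 45.9% | 1.03, 48.8% | 2.05, 24.2% |
| 364 days (52 weeks) | 4.55, 4.3% | 4.18, 5.5% | 8.27, 0.3% |

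The ±3-day windows on Days 180 and 270 make the completer's interval 84 to 96 days. At *h* = 80–87 that is 0.97 to 1.20 half-lives, with 51.2% down to 43.5% remaining.

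**Load in dose equivalents for a completer.** Assume first-order elimination and simple superposition, ignoring absorption lag. With *r* = 0.5^(30/*h*), the load just after the seventh dose is 120 × (1 − *r*^7)/(1 − *r*).

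- *h* = 80: *r* = 0.771, sum = 3.66, so 439 mg at Day 180. At 90 days, 439 × 0.459 ≈ 201 mg.
- *h* = 87: *r* = 0.787, sum = 3.82, so 458 mg at Day 180. At 90 days, 458 × 0.488 ≈ 224 mg.
- *h* = 44: *r* = 0.623, sum = 2.56, so 307 mg at Day 180. At 90 days, 307 × 0.242 ≈ 74 mg.

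All three exceed the 30 mg single-dose level above which Section 1.2.3 reports maximal pSTAT3 suppression. At 52 weeks the load is 439 × 0.043 ≈ 19 mg (*h* = 80) to 458 × 0.055 ≈ 25 mg (*h* = 87), below that level.

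The milligram figures apply to a patient who received all seven 120 mg doses. An early leaver has had fewer, so only the percentages carry over.

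**The case against.** The strongest objection is that the document shows nothing to be wrong. It does not say that a live-vaccine interval must scale with half-life, and the risk of a live vaccine on this drug cannot be quantified from it. A reader might infer that the protocol contradicts itself by using 52 weeks or five half-lives elsewhere. It does not. The contraception rule guards against fetal exposure, where Section 1.2.5.9 adds that "No data on preclinical reproductive toxicity are available at the time of this study". The prior-study exclusion ("clinical study within 30 days or 5 half-lives of baseline, whichever is longer") and Appendix 4 ("WASHOUT TIMES OF MEDICATIONS BASED ON 5 HALF-LIVES") concern other treatments before entry. These show that the sponsor uses half-life when setting intervals; they do not set this one.

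A reader might also infer that the two-month clause is a drafting error because it is inactive for an on-schedule completer. That does not follow either. Under Section 3.5 a patient who discontinues may be at end of study at once, and the clause then acts as a floor. Section 5.5 still directs a 90-day visit for such patients, so how the two sections interact is open.

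Three further limits stand. The 80–87 days come from single doses in healthy subjects, and no half-life in SLE patients is shown. The 30 mg reference is also a single-dose finding. Some text points the other way: anti-tetanus antibody was unaffected in monkeys (Section 1.2.5.7) and no untoward safety signal was seen at the MAD interim (Section 3.1.2.1), although neither observation concerns live vaccines.

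These limits reduce certainty about the size of the problem but do not remove it. Even on the 44-day figure, the completer's modelled load at release is above 30 mg.

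**Conclusion.** The point holds as a cheap patient-safety improvement, severity CONSIDER. Item 6 releases a completer after 1.03–1.13 half-lives on the final pharmacokinetic estimate. The modelled residual load is then larger than one full 120 mg dose, and it lies above the protocol's own threshold for maximal target suppression under either printed half-life. That goes beyond a missing rationale, because following the rule as written permits live vaccination while the protocol's data suggest continuing IL-21 blockade.

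The conclusion rests on these assumptions: the study's course means individual participation (on a whole-trial reading the ban would last longer for early enrollees); elimination is first-order with doses adding; and the healthy-subject half-life carries over to patients. Nothing here establishes an actual rate of vaccine-related harm, and alpha, power and the analysis are untouched. Whether patients are given longer vaccine advice in the consent form or the Investigator's Brochure cannot be judged, because neither is available here.

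**What to change.** In Section 4.6.2, item 6, keep the 30-day pre-screening rule and the bar during the study, and replace the two-month tail with 52 weeks after the last dose. For example: *live vaccines are barred throughout the study and for 52 weeks after the last dose of study drug*. This is the interval already tied to half-life in Section 4.7.2, and it leaves 4–6% of the end-of-dosing load at 80–87 days. It falls short of five half-lives (400–435 days) but brings the modelled load below 30 mg.

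The cost is one clause in an amendment. All patients wait longer for live vaccines, including the third on placebo (110/3 ≈ 37) unless they are unblinded. The rule would run 364 − 90 = 274 days, or 39 weeks, past Day 270. Under Section 4.6, concomitant medication is recorded only until the last follow-up visit, so beyond that point the rule works as advice and cannot be monitored. There is no analysis cost.

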4.7 Women of Childbearing Potential

WOCBP is defined as any woman who has experienced menarche and who has not undergone surgical sterilization (hysterectomy, bilateral tubal ligation, or bilateral oophorectomy) and is not postmenopausal.

See [Section 4.7.2](#) for detailed information regarding contraceptive requirements for WOCBP.

4.7.1 Determination of Menopause

Menopause is defined as at least 12 months of amenorrhea in a woman over age 45 in the absence of other biological or physiological causes. Women under the age of 55 years must have a documented serum FSH level > 40 mIU/mL at screening to confirm menopause.

4.7.2 Contraception

WOCBP must agree to follow instructions for method(s) of contraception for the duration of treatment with study drug plus 52 weeks, due to the mean terminal $\frac{1}{2}$ life of the study drug.

Men who are sexually active with WOCBP must agree to follow instructions for method(s) of contraception for the duration of treatment with study drug plus 52 weeks, due to the mean terminal $\frac{1}{2}$ life of the study drug.

Investigators shall counsel WOCBP and men who are sexually active with WOCBP on the importance of pregnancy prevention and the implications of an unexpected pregnancy. Investigators shall advise WOCBP and men who are sexually active with WOCBP on the use of highly effective methods of contraception. Highly effective methods of contraception have a failure rate of < 1% when used consistently and correctly.

- Patients must agree to either complete abstinence, defined as a complete avoidance of heterosexual activity, or the use of 2 methods of effective contraception from the following:
- Male condoms with spermicide
- Diaphragm with spermicide
- Cervical cap with spermicide
- Hormonal methods of contraception including combined oral contraceptive pills, vaginal ring, injectables, implants, patches and intrauterine devices (IUDs) such as Mirena® by patients who are WOCBP or a male patient's WOCBP partner. Women who are partner of men who are patients participating in the study may use hormone-based contraceptives as one of the acceptable methods of contraception since they will not be receiving study drug
- IUDs, such as ParaGard®
- Vasectomy
- Note: Women who are abstinent while participating in the study must continue to have pregnancy tests. Acceptable alternate methods of highly effective contraception must be discussed in the event that the patient chooses to forego complete abstinence

- Azoospermic men and WOCBP who are continuously not heterosexually active are exempt from contraceptive requirements. However, WOCBP must still undergo pregnancy testing

4.8 Deviation from Inclusion/Exclusion Criteria

Deviation from the inclusion or exclusion criteria will not be allowed. If deviation of inclusion/exclusion criteria is discovered after randomization, the Investigator should contact the medical monitor for discussion. A decision will be made whether to allow a patient to continue or withdrawal from the study medication.

See [Section 6.8](#) for additional details.

4.8.1 Patient Withdrawal and Replacement

See [Section 5.5](#) for reasons for removal from the trial. Withdrawn patients may be replaced during the MAD part of the study after discussion between the Principal Investigator or designee and sponsor.

5 STUDY PROCEDURES

Refer to the eCRF completion guidelines for data collection requirements and documentation of study assessments/procedures.

